Study nurse prescribes fixed dose statin and/or ARB drugs (Intervention arm only). If subjects are randomized into the treatment arm and are already taking either a statin or any anti-hypertensive medication, they will be prescribed only the drug they are not already taking (e.g. participants on a statin will be prescribed only losartan). If subjects are already taking either a statin or anti-hypertensive medication, we will not alter the dosage of the previously prescribed medication.

We will send letters about the trial to the subject's PCP, regardless of subject's randomization.

Intervention arm subjects will get an additional blood draw in-between the medication visit and first follow-up visit to ensure it is safe for them to continue taking the study medications.

Step 4: Follow-up Visits (every 3 months for 12 months)

RAs conduct follow-up interviews, perform pill counts, and collect urine pregnancy tests (all arms)

Study nurses collect blood samples and vital signs; conduct safety checks; track visits (dates, clinician type), diagnoses, prescription drugs (names, doses, pill counts of cardiovascular drugs), and medical events (all arms)

Study nurses will record and reconcile medication lists at every visit, and note changes in medications.

Study nurse prescribes additional fixed dose statin and/or ARB drugs (Intervention arm only).

Participants who have baseline CK values within 2*ULN will be enrolled in the study. If these participants are randomized into the treatment arm, and will be receiving treatment with a statin, they will be asked to come for additional safety blood draws once per month in addition to one draw one week following the first dose of study drugs. This draws will be done to ensure participant safety while taking the study medications. If a trend of increasing CK is observed, the study medications will be discontinued (Intervention arm only).

Participants prescribed the ARB who exhibit symptoms of hypotension (e.g., syncope, dizziness) and/or have an SBP measurement of <100 mmHg at the follow-up visit will additionally be evaluated for orthostatic hypotension and tachycardia. Study PIs will be notified, and will make a decision based on these criteria to either continue or discontinue the ARB at this time. These participants will be asked to come back within one week of their follow-up visit for an additional blood pressure check. (Intervention arm only).

Step 5: Final Assessment

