receiving treatment for increased cardiovascular risk (i.e. subjects who are already prescribed either a statin or ARB drug). In this case, subjects will be given the remaining non-prescribed medication (e.g. subjects already receiving treatment with a statin will be prescribed losartan, and subjects receiving any anti-hypertensive treatment will be prescribed simvastatin). We will not alter the dosing of any previously prescribed medication, including any statin or anti-hypertensive medications. Subjects who are already receiving both medications, will be included in the non-randomized group. We will include patients with state appointed legal guardians or health proxies with durable power of attorney who have the specific authority to make mental health care decisions or to consent to participate in research. Guardians or proxies will use substituted judgment when deciding to enroll the patient in this research study. State sponsored legal guardians are the preferred surrogate, however, we will accept health care proxies with durable power of attorney; no other form of surrogate will be accepted, participants with other forms of surrogates that are unable to provide consent on their own will be excluded. The relationship between the participant and surrogate will be recorded on the informed consent form that all parties have signed. We will include patients who cannot speak English. We will follow the PHRC policy on Obtaining and Documenting Informed Consent of Subjects who do not Speak English as found on the PHRC website at http://navigator.partners.org/ClinicalResearch/Non-English Speaking Subjects.pdf. An attempt to administer all aspects of the proposed research will be made through the use of an official translating service (i.e. electronic, phone, or in person translator). The consenting process for non-English speakers will always be done in the presence of an official hospital translator when using the short from consent procedure. Any measures that are invalidated by translation will be discarded during analysis. Since our primary measures are adherence, evidence through pill counts and improvement in metabolic risk factors, there is still value to the study and the subject to participation of non-English speakers.

Other inclusion criteria include the following:

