Characterization of Usual Treatment: We also will carefully describe care under Usual Treatment, including the timing of initiation, treatment choice, adherence, prescribing clinicians, and visit patterns for subjects in the control arm. We will characterize the involvement of other clinicians for subjects in both arms, and clinic traits.

Treatment Operational Definition: To start, we will use the same treatment definition for both study arms, i.e., current use of a statin and angiotensin drug. Because there are multiple potential drugs for cardiovascular prevention, we will alter this definition in a series of sensitivity analyses. For example, we will examine a minimal cardiovascular treatment variable in which we define treatment as current use of any cardiovascular drug, independent of the therapeutic class or mechanism of action. We also will examine a partial treatment variable in which we count the number of distinct cardiovascular prevention drugs.

Analysis approach 1: We will plot the percent on "adequate" CVD prevention care, at baseline and the four quarterly follow up times to monitor how treatment activity unfolds over time in the two arms of the trial. At any given follow-up point we will be comparing

two binary outcomes (on or off treatment) and will use standard methods for comparing two proportions to test statistical significance and get confidence intervals for the difference in the percent on treatment in the two arms. We will use a Bonferroni correction so the four separate tests or CIs will have an overall level of 0.05 or 95% CI, respectively.

Analysis approach 2: We will use all available follow-up data to construct a summary measure of the mean percentage of follow-up time during which each group was on treatment. Since we expect the distribution of outcomes to be non-normally distributed, we will get a test of significance for no difference between the mean outcomes in the two arms using a randomization test. A 95% confidence interval for the difference of percentage of time on Tx will be obtained using bootstrap methods. We will use STATA 13.0 for all analyses.

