Analysis of Aim 3: Per-Protocol Effect on Cardiovascular Risk Factors: For Aim 3, we will study the same composite and individual risk factor outcomes as for Aim 2, but will estimate the per-protocol effect rather than the ITT effect. ITT is the effect of assignment to the strategies of interest; the per-protocol effect is the effect of following the strategies as indicated in the protocol and is the implicit target of inference. To estimate the per-protocol effect, however, one needs to make assumptions similar to those commonly made in the analysis of observational studies. Specifically, when adjusting for measured covariates, the valid estimation of the per-protocol effect requires that all fixed and time-varying factors that jointly predict the outcome and adherence to the assigned intervention are measured without error. We will adopt two analytic approaches, both involving adjustment via inverse probability (IP) weighting. Analysis approach 1: We will artificially censor participants when they stop adhering to the assigned strategy. We will censor subjects in the active treatment arm if/when their adherence drops below 80% of the intended dose, based on estimates of the proportion of days covered (PDC). [141-144] In sensitivity analyses, other adherence cutoff points will be used, as in our other past studies.^[145] For subjects in the control arm, we will follow two censoring strategies: (i) subjects will be censored if/when they start taking one of the drugs assigned to the active treatment arm, (ii) subjects will never be censored, which is equivalent to interpreting any treatment they receive as standard of care. We will conduct separate analyses under each of these two censoring strategies. We will compare the average outcome between arms at pre-specified time points during the follow-up. The outcome models will be similar to those described for Aim 2, but they will be fit to those remaining uncensored at the corresponding time. This approach requires no assumptions about the dose-response curve for adherence because only adherent subjects contribute to the fit of the outcome model.

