**NCT02188121**

Protocol Title: Clinical trial to reduce cardiovascular health risks in  
patients with serious mental illness

Statistical Analysis Plan Date: 02/10/2018

Background: This trial focuses on SMI patients who are potentially eligible for cardiovascular prevention therapy (through statin and angiotensin medications such as angiotensin receptor blockers or ARBs) but who have not yet received it. The trial compares a prevention strategy intervention with usual care with respect to use of therapy. The trial includes those on partial therapy and excludes those with detected cardiovascular disease or diabetes, and assesses whether the intervention increases cardiovascular prevention use relative to usual care.

Eligibility summary: Eligibility criteria include a diagnosis of schizophrenia, schizoaffective disorder, or bipolar disorder; second generation antipsychotic (2GA) therapy within the past six months before trial entry; and mental health care at one of the study sites at the time of trial entry. We exclude subjects who already have a diagnosis of diabetes or cardiovascular disease; who already are receiving therapy with both statins and angiotensin medications (i.e., the same therapeutic drug classes as used in the intervention); or who have contraindications to both drug classes.

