Primary study outcome: The main outcome is use of the cardiovascular prevention medications over the 12-months after study initiation. For each individual, we define the primary outcome as the proportion of the 12 follow-up months during which she/he either received any of the prescribed medication or the medication became clinically contraindicated after trial entry (as decided by the treating physician). We will assess the outcome using medication counts at each study visit (i.e., at the 3-, 6-, 9-, and 12-month study visit), supplemented by subject self-reports and the clinic chart review. For subjects who are eligible to receive both statins and ARB medications at baseline, we will calculate the number of days that they receive both medications during the 12 months of follow-up. For subjects who are eligible to receive only one of the two medications at baseline (i.e., because of pre-existing therapy with or because of contraindications to the other prevention medication before trial entry), we will calculate the number of days that they receive the medication during the 12 months of follow-up, with the same approach for addressing changes in subsequent eligibility.

Analysis of the primary study outcome: The primary analysis will follow the intention-to-treat (ITT) principle. We will use regression analysis to estimate the mean average of the primary outcome in each group and the difference between the mean outcomes, along with its 95% confidence interval and using the p-value for a null hypothesis. If clinically meaningful imbalances are detected in baseline covariates despite randomization, we will adjust for those covariates. If necessary, we will adjust for selection bias due to loss to follow-up via inverse-probability weighting. In supplemental analyses to the main ITT approach, we also will conduct appropriately adjusted per-protocol analyses. We will use STATA 13.0 for all analyses. We also will examine a number of pre-specified subgroup analyses, in which we examine whether the intervention might be more effective among those SMI patients who are more likely to receive fragmented care or less likely to be adherent to complex treatment regimens, e.g., SMI patients with Medicaid versus those with commercial health insurance.

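### The blood pressure component is defined differently at entry, in outcome scoring and in Aim 3 censoring, so the primary difference can be misstated in either direction

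*SAP*

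**What the plan says.** **Entry.** Protocol Table 1, Step 3, covers intervention participants who are "already taking either a statin or any anti-hypertensive medication, they will be prescribed only the drug they are not already taking". Protocol section III (Eligibility) repeats the rule by example: "subjects receiving any anti-hypertensive treatment will be prescribed simvastatin". The sentence just before that example is narrower and speaks of a statin or an ARB.

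**Exclusion.** The SAP Eligibility summary excludes people "who already are receiving therapy with both statins and angiotensin medications". The SAP Background gives ARBs as an example of angiotensin medications.

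**Treatment definition.** Protocol section VI (Treatment Operational Definition) starts from "current use of a statin and angiotensin drug" in both arms. It adds sensitivity analyses that count any cardiovascular drug, or the number of distinct drugs. The SAP does not repeat them.

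**Primary outcome.** The SAP first defines the outcome as the proportion of months in which the person "received any of the prescribed medication or the medication became clinically contraindicated after trial entry". It then says that for those "eligible to receive both statins and ARB medications at baseline, we will calculate the number of days that they receive both medications". Participants open to only one drug, "because of pre-existing therapy with or because of contraindications to the other prevention medication before trial entry", are scored on that drug.

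**Aim 3.** Under the first of two strategies for the control arm (approach 1), "subjects will be censored if/when they start taking one of the drugs assigned to the active treatment arm". Under the second, controls are never censored.

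**The concern.** The same drug can have a different status depending on when it was started. An antihypertensive outside the scored class fills the blood pressure component if it is taken at entry, but earns nothing if it is started afterwards.

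The arms are not equally exposed to this. When an intervention participant qualifies for the blood pressure drug, the study supplies losartan or valsartan, and both are ARBs. A control receives whatever the usual clinicians choose. A narrow class can therefore miss real treatment more often among controls.

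At stake are the meaning of the primary difference and the composition of the untreated comparator in Aim 3. The trial is open-label. If the qualifying drugs are left open, they could be settled after use patterns are visible, despite the commitment in the Aim 2 section to finalise the analysis before looking at outcome data.

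**Working it through.** The documents give no figure for the effect of the class definition, so there is none to reproduce. I take the participant types in turn and then bound the size.

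**Participant types**

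1. *Enters on a statin and is scored on the ARB alone.* A control whose clinician starts a non-ARB antihypertensive scores no days. Only one component is open, so the choice between *any* and *both* does not help. This is the clearest case. Reading the class as all angiotensin drugs narrows the gap but leaves other antihypertensives uncredited.
2. *Enters on neither drug and is open to both.* A control who starts a statin plus a non-ARB antihypertensive scores nothing under *both*, but could be credited for the statin under *any*. A control who starts only a blood pressure drug scores nothing under *both* even if it is an ARB, so that loss is not a class problem.
3. *Enters on a non-ARB antihypertensive and, in the intervention arm, is given only simvastatin.* The SAP's one-drug rule needs prior therapy with, or a contraindication to, the other prevention medication. If that means an ARB, prior use of another agent does not trigger the rule. The participant could then be held to days on both drugs although the study never supplied the ARB.
4. *Participants properly scored on the statin alone* are unaffected by the blood pressure class.
5. *Aim 3, first strategy.* A control who starts a statin or angiotensin drug other than those assigned is not censored and stays as an untreated comparator. If the drug lowers that person's LDL or blood pressure, the contrast between arms shrinks.

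**Possible overstatement (types 1 and 2)**

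Inputs:
- Control initiation: below 15% (Protocol, Power Calculations); 0.15 is used as the upper value.
- s: share of those controls whose regimen would count if any antihypertensive were credited, but does not count under the ARB wording. Not given; range 0 to 1.
- t: fraction of the 12 months on that regimen. Not given; 0.5 and 1 shown.

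Overstatement of the mean difference = 0.15 × s × t.

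| s | t = 1 | t = 0.5 |
|---|---|---|
| 0 | 0 points | 0 points |
| 0.25 | 3.75 | 1.88 |
| 0.50 | 7.5 | 3.75 |
| 0.75 | 11.25 | 5.62 |
| 1 | 15 | 7.5 |

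The protocol does not say how its 15% defines initiation. If it already means a statin plus an angiotensin drug, regimens outside that class are not part of it and 15% is the wrong base. The table is an illustration, not an estimate.

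**Possible understatement (type 3)**

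Let b be the share of participants of this type in each arm (not given; 5% to 20% assumed) and D the difference they would otherwise show. For D, I borrow 20 points, one of the two differences in Power Calculations. If they score nothing in either arm, the overall difference falls by b × D:
- 0.05 × 20 = 1.0 point
- 0.10 × 20 = 2.0 points
- 0.20 × 20 = 4.0 points

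**The case against.** The strongest defence is that a class-specific endpoint is a legitimate estimand. The SAP ties its exclusion to the drug classes used in the intervention, the protocol applies one treatment definition to both arms, and a prescribing rule at entry need not decide outcome credit. That stands as an argument against making any antihypertensive the primary credit. It does not settle which class is meant, or how to score someone whose blood pressure component was treated as filled at entry by a drug outside it.

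A reader might infer more: that only ARBs count, that controls on other agents always score zero, and that the effect is therefore inflated. The documents do not support this.
- The SAP Background presents ARBs as an example of the class, so other angiotensin drugs may be intended.
- The *any* wording could credit a control for the statin. That wording is itself unclear for controls, to whom the study prescribes nothing.
- The bias is not one-directional. Type 3 shrinks the primary difference, and the Aim 3 rule dilutes rather than inflates. Intervention participants can also lose credit, because the protocol expects later changes by primary care physicians.
- Nor do the documents support the idea that the mismatch alone could produce a positive trial. All intervention participants are meant to start on treatment, and the power section considers differences of 20 and 26 points.

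The protocol's any-cardiovascular-drug analysis is a partial remedy. It is absent from the SAP, and because it counts drugs already taken at entry it does not isolate newly started treatment in the open component.

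**Conclusion.** The inconsistency is established from the text alone. The rules for entry, exclusion, scoring and Aim 3 censoring name different sets of drugs, and the SAP outcome paragraph gives two counting rules. Literal application can overstate the primary difference through types 1 and 2, understate it through type 3, and dilute the first Aim 3 strategy.

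The net direction and size cannot be derived. The overstatement runs from 0 to 15 points at 15% control initiation (0 to 7.5 points if such regimens last half the year), and the upper end requires every such control regimen to be non-qualifying all year. The understatement is 1 to 4 points under the assumed 5% to 20% share and a 20-point difference. The non-ARB share, time on drug and share entering on other agents are all assumptions. The ambiguity should be closed before outcome data are examined.

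**What to change.** - Reconcile Protocol Table 1 (Step 3) and section III with the protocol's treatment definition and the SAP on which agents fill the blood pressure component. This concerns classification only and proposes no change to what is prescribed.
- Adopt one drug-class map, identical in both arms, for entry status, outcome scoring and Aim 3 censoring.
- Set each participant's scored components from what was left open at entry under the protocol's Step 3 and section III rule. Someone given only simvastatin because of an existing antihypertensive is then scored on the statin.
- In the primary outcome, credit at least the whole statin and angiotensin classes rather than ARBs alone.
- Resolve *any* versus *both* in the SAP, and say what the *any* wording means for controls.
- Add to the SAP a sensitivity analysis that credits any newly started drug that the protocol would have counted at entry.
- In the first Aim 3 strategy, censor controls at the start of any drug in the mapped classes.

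The cost is SAP wording and a lookup table. Names, doses and pill counts of cardiovascular drugs are already recorded at follow-up visits in all arms. The downside is that the primary difference may come out slightly smaller.
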